6.6.1.2 Guidelines for Dose Modification: Specific Non-hematologic Toxicities

Adverse Event	Grade	Camidanlumab Tesirine Management Guideline
Infusion-related reactions	1	
The infusion rate may be decreased or temporarily interrupted to permit resolution of the event. If the total time for dilution into the IV bag and infusion takes longer than 4 hours, the remaining solution of camidanlumab tesirine will be discarded and the dosing will continue with the assigned dose at the next scheduled dosing visit.
 
Please refer to Section 6.9.4 for treatment recommendation.

Adverse Event	Grade	Camidanlumab Tesirine Management Guideline
	2	
Interrupt camidanlumab tesirine infusion to permit resolution of the event. If the event resolves within the total time of 4 hours after dilution into the IV bag and infusion time, resume camidanlumab tesirine infusion at 50% of the prior infusion rate, still not exceeding the total of 4 hours after infusion has restarted.
 
If the resolution takes longer than the total 4 hours, the remaining solution of camidanlumab tesirine will be discarded, and the dosing will continue with the assigned dose at the next scheduled dosing visit at 50% of the prior infusion rate.
 
Please refer to Section 6.9.4 for treatment recommendation.

	3	
Permanently discontinue camidanlumab tesirine.
 
However, if the AE resolves within 24 hours after onset (with or without clinical management), dosing may continue with the assigned dose at the next scheduled dosing visit at 50% of the prior infusion rate.
 
Please refer to Section 6.9.4 for treatment recommendation.

	4	Permanently discontinue camidanlumab tesirine.
AST, ALT, or GGT abnormalities or Edema or Effusion	2/3	
First Occurrence: Hold camidanlumab tesirine until improvement to \leqGrade 1 or Baseline.
 
If improvement to \leqGrade 1 or Baseline occurs prior to the next scheduled dose, continue camidanlumab tesirine at the original assigned dose level in subsequent treatment cycles.
 
If improvement to \leqGrade 1 or Baseline occurs >21 days from the last scheduled (but missed) camidanlumab tesirine dose, continue camidanlumab tesirine and reduce by 1 dose level from the original assigned dose in subsequent treatment cycles.
 
Second Occurrence: Hold camidanlumab tesirine until improvement to \leqGrade 1 or Baseline.
 
If improvement to \leqGrade 1 or Baseline occurs prior to the next scheduled dose, reduce by 1 dose level from the original assigned dose in subsequent treatment cycles.
 
If improvement to \leqGrade 1 or Baseline occurs >21 days from the last scheduled (but missed) camidanlumab tesirine dose, continue camidanlumab tesirine and reduce by 2 dose levels from the original assigned dose in subsequent treatment cycles.
 
Otherwise, camidanlumab tesirine should be permanently discontinued.
 
Third Occurrence: Permanently discontinue camidanlumab tesirine.

Adverse Event	Grade	Camidanlumab Tesirine Management Guideline
	4	
First Occurrence:
 
Hold camidanlumab tesirine until improvement to \leqGrade 1 or Baseline.
 
If improvement to \leqGrade 1 or Baseline occurs prior to the next scheduled dose, continue camidanlumab tesirine and reduce by 1 dose level from the original assigned dose in subsequent treatment cycles.
 
If improvement to \leqGrade 1 or Baseline occurs >21 days from the last scheduled (but missed) camidanlumab tesirine dose, continue camidanlumab tesirine and reduce by 2 dose levels from the original assigned dose in subsequent treatment cycles.
 
Otherwise, camidanlumab tesirine should be permanently discontinued.
 
Second Occurrence:
 
Permanently discontinue camidanlumab tesirine.

Hy's law (AST and/or ALT $> 3 \times$ ULN and bilirubin $> 2 \times$ ULN)	-	
Permanently discontinue camidanlumab tesirine.
 
Hy's law defined as: AST and/or ALT $>3 \times$ ULN and bilirubin $>2 \times$ ULN, and without initial findings of cholestasis (ALP activity $<2 \times$ ULN) and no other reason that could explain the combination of increased transaminases and serum total bilirubin, such as viral hepatitis A, B, or C, preexisting or acute liver disease, or another drug capable of causing the observed injury.

Autoimmune toxicities (e.g., hypothyroidism, hyperthyroidism, hepatitis, other endocrinopathies)	≥ 1	
Need to be followed at least weekly to quickly detect deterioration and modify dosing as per general recommendations in Section 6.6.1.1 (can be done by telephone unless symptoms worsen).
 
Consider using American Society of Clinical Oncology (ASCO) guidelines for management of immune mediated toxicities (Brahmer, 2018, or local guidelines).
 
Specific guidelines for management of hyperthyroidism, hypothyroidism, and hepatitis are provided in the Appendix 13.5.

Selected Types of Infection: HSV1, HSV2, VZV, EBV, CMV, measles, Influenza A, Zika virus, Chikungunya virus, mycoplasma pneumonia, Campylobacter jejuni, enterovirus D68, or SARS-CoV-2.	Any Grade	
No dose adjustment is required; however, hold camidanlumab tesirine. Re-dosing must be delayed so that there is at least a 4-week window between symptom resolution and the next dose of camidanlumab tesirine.
 
If there is suspicion that a patient may have contracted the coronavirus disease COVID-19 (e.g., recent contacts with persons who tested positive and/or recent symptoms of respiratory tract infection and/or recent loss of smell and/or taste), a pathogen-directed SARS-CoV-2 test, such as PCR, should be performed. If the patient tests positive, a repeat test should be conducted 7 to 14 days later. If the patient repeatedly tests positive without having developed symptoms, dosing may proceed at the discretion of the Investigator.

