- Schedule 1: Administration of camidanlumab tesirine for the first 2 cycles with concomitant administration of pembrolizumab starting at the first cycle (additional administrations of camidanlumab tesirine according to a schedule with 2 cycles off – 2 cycles on, if there is no delay in the planned treatment schedule, or, in case of delay in the administration of pembrolizumab, after respecting a minimum of 63 days (9 weeks) between the last dose of camidanlumab tesirine and the first dose of the 2 subsequent additional administrations of camidanlumab tesirine; between these Cycles, patients should receive pembrolizumab as a single agent)
- Schedule 2: Administration of camidanlumab tesirine for the first 2 cycles with concomitant administration of pembrolizumab in the second cycle followed by pembrolizumab monotherapy thereafter (additional administrations of camidanlumab tesirine upon informing the Sponsor)
- The dose-escalation part will start with Schedule 1, then:
 - Schedule 2 may be initiated if dose level -1 and dose level -2 used in Schedule 1 are presenting safety concerns (e.g., significant overlapping toxicities) and investigation of Schedule 1 is stopped.
 - Other Schedules may be investigated based on observed safety and efficacy data.

No intra-patient dose-escalation is allowed in this regular dose-escalation part of the study. The number of dose levels will depend on the emergent toxicity profile of camidanlumab tesirine and will be decided by the DESC (Section 4.1.3); PK [REDACTED] may also inform decision making.

The DESC may expand enrollment at doses below the current dose level being evaluated as part of the dose-escalation process; additional patients, of the same indication, may only be added at dose levels that are equal or higher to the dose level for which at least 1 patient with documented PR or CR has been observed. No more than 10 patients in total can be treated at such dose level unless ≥ 3 of the 10 patients have documented PR or CR.

The dose-escalation part will be completed once the recommended dose(s) (and schedule[s]) for expansion (RDE)/MTD has been identified. Dose-escalation cohorts may enroll approximately 48 patients.

Paired-biopsy cohorts: Separately, paired-biopsy cohorts will enroll patients, only treated with camidanlumab tesirine as monotherapy, who will be undergoing two mandatory biopsies, one pre- and one on-treatment biopsy, [REDACTED]

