4.1.2 Dose-Expansion

Two groups are planned in the dose-expansion part (Part 2):

- Group 1: an indication for which camidanlumab tesirine in combination with pembrolizumab was shown in Part 1 to have preliminary activity.
- Group 2: a basket group of patients with advanced solid tumors and MSI-H/dMMR status, who have received a prior regimen containing a PD-1/PD-L1 inhibitor, for which the best response was CR, PR, or SD ≥ 4 months, and then progressed while under treatment with a PD-1/PD-L1 inhibitor based regimen; no more than 4 patients with the same indication are allowed in this basket group.

Part 2 will enroll approximately 30 patients, approximately 16 patients in Group 1 and 14 in Group 2.

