6.6.1.1 Camidanlumab Tesirine Dose Modification Guidelines: General Toxicities

AE Grade	Camidanlumab Tesirine Management Guideline
1/2	No dose adjustment is required.
3/4	
First Occurrence:
 
Hold camidanlumab tesirine until improvement to \leqGrade 1 or Baseline.
 
If improvement to \leqGrade 1 or Baseline occurs prior to the next scheduled dose, continue camidanlumab tesirine at the original assigned dose level in subsequent treatment cycles.
 
If improvement to \leqGrade 1 or Baseline occurs >21 days from the last scheduled (but missed) camidanlumab tesirine dose, continue camidanlumab tesirine and reduce by 1 dose level from the original assigned dose in subsequent treatment cycles.
 
Second Occurrence:
 
Hold camidanlumab tesirine until improvement to \leqGrade 1 or Baseline.
 
If improvement to \leqGrade 1 or Baseline occurs prior to the next scheduled dose, reduce by 1 dose level from the original assigned dose in subsequent treatment cycles.
 
If improvement to \leqGrade 1 or Baseline occurs >21 days from the last scheduled (but missed) camidanlumab tesirine dose, continue camidanlumab tesirine and reduce by 2 dose levels from the original assigned dose in subsequent treatment cycles.
 
Otherwise, camidanlumab tesirine should be permanently discontinued.
 
Third Occurrence:
 
Permanently discontinue camidanlumab tesirine.

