	3	
Hold camidanlumab tesirine until improvement to \leqGrade 1 or Baseline and consider dermatology consult.
 
Topical treatment to affected areas is indicated and consider systemic corticosteroid treatment e.g., prednisone 0.5 mg/kg for 10 days:
 
 - maculopapular rash or photosensitivity rash: high potency topical steroid cream BID (e.g., clobetasol propionate 0.05%, halobetasol propionate 0.05%) and consider prednisone 0.5 mg/kg for 10 days. - pruritus: high potency topical steroid cream BID (e.g., clobetasol propionate 0.05%, halobetasol propionate 0.05%) and consider oral antipruritic (e.g., hydroxyzine, gabapentin, or pregabalin). - xerosis or hyperpigmentation: consider ammonium lactate 12% or urea 20% BID; and triamcinolone 0.1% cream BID. 
Reassessment every 2 weeks is indicated (either by healthcare professional or patient self-report); if reactions do not improve, then:
 
First Occurrence:
 
 • If improvement to \leqGrade 1 or Baseline occurs prior to the next scheduled dose, proceed with the originally planned camidanlumab tesirine dose level. • If improvement to \leqGrade 1 or Baseline occurs >21 days from the last scheduled (but missed) camidanlumab tesirine dose, reduce by 1 dose level from the original assigned dose in subsequent treatment cycles. 
Second Occurrence:
 
 • If improvement to \leqGrade 1 or Baseline occurs prior to the next scheduled dose, reduce by 1 dose level from the original assigned dose in subsequent treatment cycles. • If improvement to \leqGrade 1 or Baseline occurs >21 days from the last scheduled (but missed) camidanlumab tesirine dose, reduce by 2 dose levels from the original assigned dose in subsequent treatment cycles.

Adverse Event	Grade	Camidanlumab Tesirine Management Guideline

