	4	
 Otherwise, camidanlumab tesirine should be permanently discontinued. 
Third Occurrence: Permanently discontinue camidanlumab tesirine.
 
Hold camidanlumab tesirine until improvement to \leqGrade 1 or Baseline and consider dermatology consult.
 
Topical treatment to affected areas is indicated and consider systemic corticosteroid treatment e.g., prednisone 0.5 mg/kg for 10 days:
 
 maculopapular rash or photosensitivity rash: high potency topical steroid cream BID (e.g., clobetasol propionate 0.05%, halobetasol propionate 0.05%) and consider prednisone 0.5 mg/kg for 10 days. pruritus: high potency topical steroid cream BID (e.g., clobetasol propionate 0.05%, halobetasol propionate 0.05%) and consider oral antipruritic (e.g., hydroxyzine, gabapentin, or pregabalin). xerosis or hyperpigmentation: consider ammonium lactate 12% or urea 20% BID; and triamcinolone 0.1% cream BID. 
Reassessment every 2 weeks is indicated (either by healthcare professional or patient self-report); if reactions do not improve, then:
 
First Occurrence:
 
 If improvement to \leqGrade 1 or Baseline occurs prior to the next scheduled dose, continue camidanlumab tesirine and reduce by 1 dose level from the original assigned dose in subsequent treatment cycles. If improvement to \leqGrade 1 or Baseline occurs >21 days from the last scheduled (but missed) camidanlumab tesirine dose, reduce by 2 dose levels from the original assigned dose in subsequent treatment cycles. Otherwise, camidanlumab tesirine should be permanently discontinued. 
Second Occurrence: Permanently discontinue camidanlumab tesirine.

Blistering rash	1	
No dose adjustment is required and monitor for change in severity. Consider dermatology consult
 
Topical treatment to affected areas is indicated, e.g., silvadene 1% cream BID and consider laboratory testing for blistering disorder (VZV/HSV and bacterial infection; bullous pemphigoid; pemphigus).
 
Reassessment every 2 weeks is indicated (either by healthcare professional or patient self-report).

Adverse Event	Grade	Camidanlumab Tesirine Management Guideline

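### Reductions in the liver/edema/effusion and skin tables count from the original dose, so a quickly resolving lower-grade repeat after a slow Grade 4 event sets a dose above the current one (minor)

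*Protocol*

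**What the plan says.** Protocol 6.6.1.2 and 6.6.1.5 set the dose after a related toxicity by grade, occurrence number and speed of recovery to Grade 1 or baseline. Below, *quick* means recovered before the next scheduled dose, and *slow* means recovered more than 21 days after the dose that was missed.

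- Liver enzymes, edema or effusion, Grade 4, first occurrence, slow: "continue camidanlumab tesirine and reduce by 2 dose levels from the original assigned dose in subsequent treatment cycles".
- Same events, Grade 2/3, second occurrence, for recovery "prior to the next scheduled dose, reduce by 1 dose level from the original assigned dose in subsequent treatment cycles".
- Same events, Grade 2/3, first occurrence, quick: "continue camidanlumab tesirine at the original assigned dose level in subsequent treatment cycles".
- Skin (the rash/pruritus/xerosis/hyperpigmentation block and the blistering-rash block), Grade 4, first occurrence, slow: "reduce by 2 dose levels from the original assigned dose in subsequent treatment cycles".
- Skin, Grade 3 (Grade 2/3 for blistering rash), first occurrence, quick: "proceed with the originally planned camidanlumab tesirine dose level". At the second occurrence, quick, the dose is one level below the original.

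Neither section says whether a reduced dose may go up again. Neither says whether a Grade 3 event that follows a Grade 4 event is a second occurrence or the first in its own row.

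The nearest general restriction is in 4.1.1: "No intra-patient dose-escalation is allowed in this regular dose-escalation part of the study". The expansion part is described in 4.1.2: "Part 2 will enroll approximately 30 patients, approximately 16 patients in Group 1 and 14 in Group 2".

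**The concern.** A dose-modification table should never send a patient who has just had a repeat toxicity to a higher dose than the one that produced it. Because each step is anchored to the original dose and takes no account of reductions already made, these two tables can do that. The patient concerned has already had a Grade 4 event with prolonged recovery and has then had the same kind of toxicity again at a reduced dose.

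The general table in 6.6.1.1 pools Grades 3 and 4 and does not behave this way. The liver and skin tables split off Grade 4 in order to be stricter, and that split creates the increase, so it is probably unintended.

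**Working it through.** The plan states no figure to reproduce. The check is an enumeration of the rules.

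**1. Levels relative to the original dose (6.6.1.2 and 6.6.1.5)**

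| Event | Quick | Slow |
|---|---|---|
| Grade 4, first occurrence | −1 | −2 |
| Lower grade, first in its row | 0 | −1 |
| Lower grade, second occurrence | −1 | −2 |

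A second Grade 4 event means discontinuation.

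**2. Grade 4 event followed by a lower-grade event of the same type**

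| Recovery (Grade 4 / lower grade) | Counted across grades | Counted per row |
|---|---|---|
| Quick / quick | −1 to −1, unchanged | −1 to 0, raised |
| Quick / slow | −1 to −2, lowered | −1 to −1, unchanged |
| Slow / quick | −2 to −1, raised | −2 to 0, raised |
| Slow / slow | −2 to −2, unchanged | −2 to −1, raised |

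Slow then quick raises the dose under both ways of counting. Starting with the lower-grade event never raises it: the dose falls, stays the same, or treatment stops. These are counts of rule combinations, not probabilities. They leave out recovery that falls between the next scheduled dose and the 21-day mark, where the Grade 4 row leads to discontinuation.

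**3. Comparison with 6.6.1.1**

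There, a slow first Grade 3/4 event leads to the instruction to "reduce by 1 dose level from the original assigned dose in subsequent treatment cycles", and a quick second event gives the same level: −1 to −1. A two-level cut comes only at a second occurrence and a third means stopping, so the same toxicity cannot raise the dose.

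**4. Slow Grade 4 then quick lower grade, in µg/kg, on the Table 5 (combination) levels**

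Rise = new dose / current dose − 1. The highest original dose shown is 150, the highest monotherapy dose reported in 1.3.4; the expansion dose is not stated.

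| Original | Current (−2) | Counted as second (−1) | Counted as first (0) |
|---|---|---|---|
| 30 | 13 | 20 (+54%) | 30 (+131%) |
| 45 | 20 | 30 (+50%) | 45 (+125%) |
| 60 | 30 | 45 (+50%) | 60 (+100%) |
| 80 | 45 | 60 (+33%) | 80 (+78%) |
| 100 | 60 | 80 (+33%) | 100 (+67%) |
| 125 | 80 | 100 (+25%) | 125 (+56%) |
| 150 | 100 | 125 (+25%) | 150 (+50%) |

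**5. Reach**

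- Protocol 1.3.4 states that monotherapy enrolment is complete. Part 2 is combination only: 16 + 14 = 30 patients.
- The raised dose would be at least the patient's third. In the combination, doses from Cycle 5 require, under 6.4, no Grade 2 or higher liver enzyme increase, pleural effusion or edema. That bars most of the 6.6.1.2 cases. Skin events are not in that list, so 6.6.1.5 is the main route.
- Grade 3 or higher rash in monotherapy was 6.8%, which is 3/44 (exact 95% CI 1.4% to 18.7%). If that rate carried over to the combination, which is an assumption, 30 × 0.068 gives about 2 patients (30 × 0.014 = 0.4 to 30 × 0.187 = 5.6). The Grade 4, slow-recovery, recurrent subset is not reported and must be smaller.

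**6. Effect of a cap**

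Taking the lower of the current dose and the table dose gives −1, −2, −2, −2 (across grades) or −1, −1, −2, −2 (per row) for the four sequences: no raise under either count.

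**The case against.** The strongest reply is that almost nobody will meet this sequence and that other text stands in the way. Much of that stands.

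- **Immune-related events.** Grade 4 immune-mediated skin events stop treatment in the combination (6.6.1.5.1). Toxicity that returns on rechallenge after a significant immune-related event stops camidanlumab tesirine (6.6.1.6). Immune-related events in the combination follow Table 14, which was not in the text available for this review. These rules do not clearly reach ordinary rash, because 8.1.1, in defining events of special interest, does not treat rashes as immune-mediated apart from named severe forms.
- **Bar on intra-patient escalation.** The sentence in 4.1.1 could be read as blocking a return upward, but it covers only the regular escalation cohorts and not Part 2.
- **Condition in the skin table.** The dose steps follow a two-weekly reassessment and apply when the reaction has not improved. Read strictly, a repeat that has improved at that check never reaches the step that resets the dose. This narrows the route. It does not close it, since a reaction unimproved at two weeks can still recover before the next dose.
- **Sponsor discussion and investigator judgment.** Section 6.6 asks for discussion with the sponsor before either drug is resumed after a hold for a related event in the combination, and that discussion might cover the dose. Section 6.6.1 leaves resumption to the investigator. Many clinicians would not read an instruction to reduce as an order to increase. These are safeguards in practice, but the written level remains the table's.

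A reader might also infer that a slow event followed by a quick one in the same row is a second fault, because the ordered reduction leaves the dose where it was. Nothing is raised in that case. Holding the dose after a faster recovery is a defensible choice, so it is not part of this point.

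**Conclusion.** The point holds as a minor drafting fault with a safety direction. On the literal text of 6.6.1.2 and 6.6.1.5, a slow Grade 4 event followed by a quick lower-grade repeat sets a dose above the one at which the toxicity recurred, however occurrences are counted. No rule in the available text clearly blocks this in Part 2.

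Three stronger readings are not supported:

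- **Overdosing beyond assignment.** The resulting dose never exceeds the original assigned dose.
- **A fault across all dose-modification rules.** The general table cannot produce the increase for the same toxicity.
- **A sizeable group at risk.** With monotherapy closed and most liver, pleural effusion and edema cases barred by 6.4, the realistic setting is non-immune skin toxicity in about 30 Part 2 patients. Well under one affected patient is plausible, although combination rates are unknown.

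The upper range of 50% to 131% depends on treating a lower-grade repeat after a Grade 4 event as a first occurrence, which is the less natural count. The 25% to 54% range does not depend on that. Both assume an original dose between 30 and 150 µg/kg on the Table 5 levels.

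**What to change.** Add one sentence to 6.6.1 at the next amendment:

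> *Camidanlumab tesirine is not re-escalated after a toxicity-related reduction; after any event the dose is the lower of the current dose and the dose given by the table.*

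This removes every raise under either counting rule and leaves the two-level limit as it is. It needs no extra patients or procedures.

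The cost is slightly lower dose intensity in a few patients. In the slow-then-quick sequence on Table 5, the next dose would be 20% lower (100 instead of 125) to 35% lower (13 instead of 20) than the table now gives if the repeat counts as a second occurrence. It would be 33% lower (100 instead of 150) to 57% lower (13 instead of 30) if it counts as a first.

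A rule that occurrences are counted across grades is not needed for this purpose and should not be added with it. It would change the stopping criteria: a lower-grade event followed by a first Grade 4 event of the same type would then end camidanlumab tesirine. Re-anchoring every step to the current dose is also unnecessary. It could take a patient three levels below the original, for example from 150 to 80.
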